##### **4.2.8.1 Adverse Events**

TEAEs will be summarised separately for the on-treatment, on-study, and post-treatment periods, as defined in Section [3.4.1](#). The primary period of interest for safety summaries will be the on-treatment period and this is the only period that will be used for the placebo controlled first 24 weeks summaries. Limited summaries will be produced for the on-study and post-treatment periods for the whole study summaries only. AEs in the pre-treatment period (with start date prior to the first dose of IP) will be listed for the placebo-controlled treatment period at primary database lock only.

All summaries will be presented by treatment group and key tables will include exposure-adjusted rates to account for any differences in follow up.

The rate of TEAEs per person-years at risk will be calculated as (number of participants reporting the TEAE) / (total IP exposure with participants at risk of TEAE) for on-treatment and on-study periods. The post-treatment AEs will be listed. The total period at risk for each participant will be the duration of the on-treatment, post-treatment and on-study periods as defined in Section [3.4.1](#). Rates will be expressed in terms of events per 100 participant-years.

An overall summary table will be produced showing the number, percentage, and exposure-adjusted rate of participants with at least 1 TEAE in any of the following categories; TEAEs, SAEs, AEs with outcome of death, and AEs leading to discontinuation of IP (DAEs). AEs will be presented for each treatment group by system organ class and preferred term, including the number and percentage of participants reporting at least one event, number of events and exposure-adjusted rates, where appropriate.

TEAEs, AEs with outcome of death, SAEs and DAEs will be summarised by system organ class (SOC) and preferred term (PT) assigned to the event by MedDRA. For each PT, the number, percentage and exposure-adjusted rate of participants reporting at least one occurrence will be presented (ie, multiple occurrences of an AE for a participant will only be counted once).

A summary of the most common (frequency of >5%) TEAEs will be presented by PT. AEs and SAEs causing discontinuation of the study treatment and SAEs causing discontinuation from the study will also be summarised.

TEAEs, SAEs and DAEs will be summarised by preferred term and investigator's causality assessment (related versus not related) and maximum intensity, including reporting of seriousness, death and events leading to discontinuation of IP, as well as other action taken related to IP. If a participant reports multiple occurrences of the same TEAE within the same study period, the maximum intensity will be taken as the highest recorded maximum intensity (the order being mild, moderate, and severe).

Other significant TEAEs will include but may not be limited to injection site reactions and hypersensitivity events. TEAEs of injection site reactions (high level term of administration and injection site) and hypersensitivity (standardized MedDRA query of hypersensitivity) will be summarised by preferred term. The summary of injection site reactions will be summarised by injection site location and number of IP administrations. The summary of TEAEs of hypersensitivity will be presented overall and repeated for events causally related to IP as assessed by the investigator. Hypersensitivity events will be listed.

Key participant information will be presented for participants with AEs with outcome of death, serious AEs, and AEs leading to discontinuation of IP. An AE listing for the safety analysis set will cover details for each individual AE. AEs ongoing at primary DBL will be presented for both primary and final DBL reporting.

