#### **4.2.4 Study treatments**

Exposure to investigational product administration will be calculated in days as:

$$(last\ dose\ date\ of\ IP - first\ dose\ date\ of\ IP + 1)$$

and will be summarised descriptively by treatment group for the safety analysis set.

The number and percentage of participants with duration of IP administration in each of the following categories will also be summarised:

- <12 weeks
- $\geq$ 12 weeks and <20 weeks
- $\geq$ 20 weeks and <36 weeks

- $\geq 36$  weeks and  $< 52$  weeks
- $\geq 52$  weeks.

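### SAP 4.2.8.1 gives the exposure-adjusted AE rate two different denominators and a unit that does not match its numerator

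*SAP*

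**What the plan says.** SAP 4.2.8.1 plans exposure-adjusted rates in the key AE tables so that differences in follow-up are allowed for. It introduces the rate as one over person-years at risk, for the on-treatment and on-study periods, and gives the formula "number of participants reporting the TEAE) / (total IP exposure with participants at risk of TEAE".

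Two sentences later it defines the time differently: "The total period at risk for each participant will be the duration of the on-treatment, post-treatment and on-study periods as defined in Section" 3.4.1. The paragraph ends: "Rates will be expressed in terms of events per 100 participant-years".

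Elsewhere the section treats the rate as one of participants. The overview table is described as "showing the number, percentage, and exposure-adjusted rate of participants with at least 1 TEAE in any of the following categories". For preferred terms, "multiple occurrences of an AE for a participant will only be counted once". The SOC and PT tables list "the number and percentage of participants reporting at least one event, number of events and exposure-adjusted rates, where appropriate", so the event count is a separate column.

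The two time definitions sit in other sections. SAP 4.2.4 ("Exposure to investigational product administration will be calculated in days as") takes the last dose date minus the first dose date plus 1. SAP 3.4.1 lets the on-treatment period run on after the last dose. It starts the on-study period at the first dose and gives it no end date, although its on-treatment rule refers to such an end. Protocol 9.4.3 mentions exposure-adjusted rates but gives no formula.

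**The concern.** The paragraph cannot be programmed without choosing between its sentences.

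Under the formula, AEs that begin after the last dose enter the numerator while the days after the last dose are left out of the denominator. The rate is then too high. The people most affected are those who stop early: someone who stops because of an AE is counted in the numerator and adds the least time. The size of the error also depends on the reporting window, so rates from different windows would not be comparable.

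The unit is a separate fault. A count that drops repeat occurrences is labelled as events and printed beside the number of events. A reader would naturally take the rate to be that number divided by time.

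**Working it through.** The documents state no AE rate and no person-time total, so there is no figure to reproduce. I computed each denominator from its own definition for a participant on the nominal schedule. Day 1 is the first dose, and Week *w* falls on day 7*w* + 1.

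**Inputs**
- IP exposure: last dose date − first dose date + 1 (SAP 4.2.4).
- Last dose before the extension at Week 20, first extension dose at Week 24 (Protocol 4.1.2); last dose of the study at Week 48 (SAP 1.1.2).
- Double-blind on-treatment time: to the day before the first extension dose, or to 30 days after the last dose if the extension is not entered (SAP 3.4.1).
- Whole-study on-treatment time: to the scheduled EOT visit (Week 52) or 30 days after the last dose, taking the earlier (SAP 3.4.1).
- On-study end: Week 60, the follow-up visit. This is my assumption.

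**Days contributed**

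| Case | IP exposure | Period in SAP 3.4.1 | Ratio |
|---|---|---|---|
| First 24 weeks, completer | 7×20+1 = 141 | 7×24 = 168 | 1.19 |
| Whole study, completer | 7×48+1 = 337 | min(7×52+1, 337+30) = 365 | 1.08 |
| On-study to Week 60, completer | 337 | 7×60+1 = 421 | 1.25 |
| Stops after dose 1 | 1 | 1+30 = 31 | 31 |
| Stops after dose 2 | 29 | 29+30 = 59 | 2.03 |
| Stops after dose 3 | 57 | 57+30 = 87 | 1.53 |

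The numerator is the same either way, so the ratio is the factor by which the IP-exposure rate exceeds the period rate. With constant true risk, the 24-week rate would also look about 10% higher than the whole-study rate (1.19/1.08 = 1.10).

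**Illustration of denominator and unit.** Assume 60 completers, 12 with at least one TEAE, and 18 events in 24 weeks; these counts are not in the documents.
- Person-years: 60×141/365.25 = 23.16 (IP exposure) or 60×168/365.25 = 27.60 (period).
- Participants per 100 participant-years: 1200/23.16 = 51.8 or 1200/27.60 = 43.5.
- Events per 100 participant-years: 1800/23.16 = 77.7 or 1800/27.60 = 65.2.
- Stopping time at first onset, assumed at mid-period on average: (48×168 + 12×84)/365.25 = 24.84 person-years, giving 1200/24.84 = 48.3.

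**Between arms.** At 24 weeks, suppose 10% or 20% of a 60-participant arm stop after dose 1. The denominator ratio goes from 1.19 to (54×168 + 6×31)/(54×141 + 6×1) = 1.22, or to (48×168 + 12×31)/(48×141 + 12×1) = 1.24. Against an arm with no early stopping, the comparison shifts by about 2% or 4%. An on-study rate is more exposed, because a one-dose participant followed to Week 60 adds 1 day instead of 421. With 10% such participants the ratio is 421/(0.9×337 + 0.1×1) = 421/303.4 = 1.39, against 1.25 with none, a shift of about 11%.

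**Stopping time at first onset.** With a constant first-event hazard *h* and *T* = 168/365.25 = 0.46 years, using full-period time gives (1 − e^(−hT))/(hT) of the first-event rate. For assumed hazards of 0.1, 0.8 and 2.0 per year this is 0.98, 0.84 and 0.65, so the rate is about 2%, 16% or 35% low.

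**The case against.** The strongest reply is that the two sentences can be read together. The paragraph first names person-years at risk and then defines the period at risk by reference to SAP 3.4.1. SAP 4.2.4 is a separate section about the exposure summary, and 4.2.8.1 does not cite it. On this reading the exposure term is loose wording, and the denominator is the duration of whichever period is being summarised. That gives a usable rate, and it may well be what is intended. It still requires setting aside the only explicit formula, and it leaves the unit wrong. Read literally, the later sentence also lists overlapping periods, since on-study contains the other two.

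A reader might go further and infer that no rate in the safety tables would be a valid incidence, or that counting participants is itself an error. The documents do not support either. Participants with at least one event over person-time at risk is a standard exposure-adjusted incidence rate, and the table descriptions in 4.2.8.1 fit it.

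Two further points stand. Whether to stop time at first onset is a choice between known rate definitions, and it matters little for rare preferred terms. The practical consequence is also limited: safety reporting is descriptive, and counts and percentages are shown as well.

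**Conclusion.** The point holds as an inconsistent specification of minor to moderate weight. If the stated formula is followed with the SAP 4.2.4 definition, a completer's rate is about 19% too high at 24 weeks and 8% too high for the whole study. The figure of about 25% for on-study rests on the assumed Week 60 end. These figures assume nominal visit timing. For a participant who stops after one dose, the on-treatment denominator is 1 day instead of 31.

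Between-arm comparisons change little unless early stopping differs between arms, and the on-study rates are the most sensitive to that. AE counts, percentages, efficacy results and hypothesis tests are unaffected. The finding does not extend to a claim that every planned rate is invalid: once numerator, denominator and unit agree, either a participant rate or an event rate is sound.

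**What to change.** Amend SAP 4.2.8.1 and 3.4.1 before the AE tables are programmed:

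- Delete the total IP exposure term from the formula.
- Use as denominator the sum of each participant's time in the period being summarised (SAP 3.4.1). Preferably stop that time at first onset of the TEAE in question, because each participant is counted once. Say explicitly which rule applies.
- Give the on-study period an end date.
- Label the rate *participants with event per 100 participant-years*. If an event rate is also wanted, define it separately as all events over full-period time and label it as events.
- State whether post-treatment AEs get rates or are only listed. The section says both that they are summarised and that they are listed, and it includes the post-treatment period in the time-at-risk sentence.

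The cost is SAP wording and one denominator derivation. Data collection, blinding and the primary analysis are not touched.

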#### **4.2.8.2 Clinical Laboratory Safety Assessments**

All protocol-specified continuous laboratory parameters will be summarised descriptively by absolute value at each visit by treatment group, together with the corresponding changes from baseline. All parameters will be summarised in SI units, except for blood eosinophil counts

which will be summarised in both SI and conventional units. Results reported by the central laboratory in conventional units will be converted to SI units for reporting.

For continuous data, the summary statistics presented will be the minimum, Q1, median, Q3, maximum, mean and SD.

Central laboratory reference ranges will be used for the identification of abnormalities, and a shift table will be produced for each laboratory parameter to display low, normal, and high values. The shift tables will present baseline and maximum/minimum on-treatment value, as applicable for each parameter and will include participants with both baseline and post-baseline data.

Shift plots showing each individual participant's laboratory value at baseline and at maximum/minimum post-baseline will be produced for each continuous laboratory variable. If any laboratory variables show any unusual features (high or low values or a general shift in the data points) at other time points, then shift plots of these data may be produced.

Data for participants who have treatment-emergent changes outside central laboratory reference ranges will be presented. This data presentation will include all visits for those participants.

Maximum post-baseline TBL elevations by maximum post-baseline ALT and AST will be presented, expressed as multiples of the upper limit of normal (ULN). TBL will be presented in multiples of the following ULN:  $\leq 1.5$ ,  $>1.5-2$ ,  $>2$ . AST and ALT will be presented in multiples of the following ULN:  $\leq 1$ ,  $>1-3$ ,  $>3-5$ ,  $>5-10$ ,  $>10$ .

Maximum post-baseline TBL will be presented ( $<2$  and  $\geq 2 \times$  ULN) and plotted against maximum post-baseline ALT ( $<3$ ,  $\geq 3-5$ ,  $\geq 5-10$ , and  $\geq 10 \times$  ULN), expressed as multiples of ULN. This will be repeated to show maximum post-baseline TBL against maximum post-baseline AST.

Data for participants who meet the biochemical criteria for Hy's law (ALT or AST  $\geq 3 \times$  ULN and TBL  $\geq 2 \times$  ULN) will be presented, which will include all visits for this subset of participants. A line plot of liver biochemistry test results (including ALP, ALT, AST, TBL, and GGT) over time will also be presented for this subset of participants. For all participants who meet the biochemical criteria for confirmed Hy's law, a SAE narrative will be produced.

For urinalysis data, a shift table will be generated to present changes from baseline to maximum/minimum post-baseline value, displaying normal and abnormal values for selected parameters and will include participants with both baseline and post-baseline data.

Any data outside the central laboratory reference ranges will be explicitly noted on the listings.

#### **4.2.8.3 Vital Signs and Physical Examination**

For vital signs data, descriptive statistics for absolute value, change from baseline and percent change from baseline will be presented for each treatment group by scheduled visit. Summary statistics for continuous variables will present n, mean, SD, Minimum, Q1, median, Q3, and Maximum.

For physical examination data, shift tables from normal to abnormal between baseline and post-baseline visits will be evaluated.

All vital sign and physical examination data will be listed.

#### **4.2.9 Tertiary/exploratory Endpoints**

Analyses for exploratory objectives will be specified below, or additionally in an exploratory analysis plan.

##### **4.2.9.1 Patient Global Impression of Severity (PGI-S)**

[figure not shown]
The change from baseline in PGI-S score at Week 12, Week 24 and Week 52 will be analysed using MMRM model as described for secondary endpoint scores above (Section [4.2.7.1](#)).

Descriptive summary statistics for scores and change from baseline will be produced by treatment group and visit.

CCI

CCI

## 5 INTERIM ANALYSES

No formal interim analysis is planned for the study.

The first analysis will be the primary analysis reported once the last participant has reached 24 weeks of follow-up in the study. The final analysis will be performed when all participants have completed the extension period of the study.

An additional analysis may be performed between the primary and final DBLs, to report data accumulating during the extension period if needed to support end of Phase 2 decision making.

Participants and investigators will remain blinded to the treatment and regimen until the final DBL.

## 6 CHANGES OF ANALYSIS FROM PROTOCOL

Section 2.1.5 Extension period analysis set is added to identify all participants who enter into the extension period.

Sections 3.3.6 and 4.2.7.6 measures of angioedema activity, analyses added inclusion of all participants and subgroup of participants with history angioedema, in addition of those with angioedema at baseline. This will provide consistency with other studies and greater understanding of the disease and IP treatment.

## 8 APPENDIX

### 8.1 Accounting for missing data

Missing data can occur due to intercurrent events like non-adherence to randomised treatment, or early discontinuation, or non-adherence of daily UPDD usage.

This section summarises how we will describe the pattern of and reasons for missing data from the study. It will also describe how we plan to account for missing data, including both the primary and sensitivity analyses to assess the robustness of the treatment effect under different underlying assumptions to account for missing data.

#### 8.1.1 Missing data description

Tabular summaries for the percentage of participants by the reason for discontinuation of randomised treatment as well as for withdrawal from the study will be presented by treatment to describe why participants discontinue from randomised treatment or withdraw from the study. The time to discontinuation of randomised treatment and withdrawal from the study will be presented using Kaplan Meier plots (overall and split by treatment related/not treatment related reason for discontinuation, as defined in [Table 11](#)). Dependent on these outputs additional exploratory analyses may be produced as deemed necessary to further understand the pattern of missing data.

Descriptive summaries of number and percentage of participants using rescue medication and change of background medications will be provided by treatment group.

For primary endpoint variable ISS7 and key secondary endpoint variable UAS7, the summaries of number and percentage of participants with missing/non-missing daily assessments will be presented by treatment group and visit. This will summarise the amount of daily responses used in the calculation of the weekly scores.

#### 8.1.2 Multiple imputation (MI) approach

Analyses will include all participants in the FAS.

The following 4 steps will be used to build the imputation datasets and perform analyses:

- 1 100 datasets with a monotone missing pattern will be obtained, induced by Markov Chain Monte Carlo (MCMC) method up to Week 24, on participants with missing data not due to reason of interest (e.g. lost-to-follow-up).
- 2 For each of the imputed datasets obtained in step 1, the remaining missing data due to reason of interest (e.g. AE) up to Week 24, will be imputed using the regression method for the monotone pattern with adjustment for covariates as for the primary model.

- 3 Each of the 100 imputed datasets will be merged with the one dataset imputed by WOCF approach, and then be analysed using the main statistical model. These 100 datasets will be saved.
- 4 Apply Rubin's rule ([Rubin DB 1987](#)) to combine analysis results (point estimates and standard errors) from 100 imputations. Descriptive statistics including number of participants, mean, standard error, and least squares (LS) means will be provided for each timepoint. In addition, difference in LS means and the corresponding 95% CIs will be provided along with the p-values for Weeks 12 and 24.

### **8.1.3 Primary analysis under the Treatment Policy Estimand using the Missing at Random (MAR) assumption**

The primary analysis for the primary endpoint of ISS7 at Week 12 allows for differences in outcomes over the study treatment period up to 12 weeks. This primary analysis includes all data until participants withdraw from the study or up to Week 24, whichever is earlier, regardless of if they discontinue from randomised treatment. The primary analysis uses the MMRM method, treatment group will be included as an explanatory variable along with the baseline ISS7 score, visit and treatment\*visit interaction, and region, as explanatory variables, and assumes that missing data is missing at random (MAR) and is a direct likelihood approach (DL).

### **8.1.4 Sensitivity analyses: Primary estimand assuming dropout reason-based multiple imputation approach**

To examine the sensitivity of the results of the primary analysis to departures from the underlying assumptions, additional analyses will be performed. As with the primary analysis the sensitivity analyses include all data until participants withdraw (up to Week 24) from the study regardless of if they discontinue from randomised treatment.

For sensitivity analyses, missing data will be imputed using controlled sequential MI methods based on pattern mixture models ([EMA/CHMP/EWP 2010](#)). This model will assume that some pre-specified subset of participants who withdraw from the study have correlations with future unobserved visits similar to participants in the placebo arm.

The following default assumptions that will be used to impute the missing data are as follows:

- (a) MAR: Assumes that the trajectory for participants who dropped out in each arm is similar to those observed in their own treatment arm. [The primary analysis already implements this approach. It will not be repeated.].
- (b) Dropout Reason-based Multiple Imputation (DRMI): Assumes that the trajectory for participants in the benralizumab arms who dropped out for a treatment related reason or severe non-compliance of protocol is similar to that of the placebo participants,

whereas the remaining participants who has dropped out are imputed assuming MAR.

A summary of reasons for participants withdrawing from the benralizumab treatment arm and the corresponding treatment arm used to calculate the imputation response rate under MAR and DRMI is given in Table 11.

**Table 11 Parameters for calculating the imputation under MAR and DRMI**

Reason for withdrawal	MAR	DRMI
Adverse Event	Benralizumab	Placebo
Development of study-specific discontinuation criteria*	Benralizumab	Placebo
Death	Benralizumab	Placebo
Severe non-compliance to protocol	Benralizumab	Placebo
Eligibility criteria not fulfilled	Benralizumab	Benralizumab
Participant lost to follow up	Benralizumab	Benralizumab
Participant decision	Benralizumab	Based on review prior to study unblinding
COVID-19	Benralizumab	Benralizumab
Other	Benralizumab	Based on review prior to study unblinding

Note: Participants in the placebo arm are imputed using the mean of the non-missing values in placebo arm.

\* Development of study-specific discontinuation criteria are based on the following: Anaphylactic reaction to the investigational product requiring administration of epinephrine; Development of helminth parasitic infestations requiring hospitalization; If 2 doses of the IP are missed during course of the study; A respiratory-related event requiring mechanical ventilation.

Some reasons for withdrawal are clearer to determine as treatment related (AEs, Death, Development of study-specific discontinuation criteria) or non-treatment related (participants lost to follow up, eligibility criteria not fulfilled). Other reasons are less clear such as participant decision and ‘Other’; a review of each participant who withdraws from the study will therefore be carried out prior to unblinding the study. Based on this review the default assumptions for DRMI as described in b) and Table 11 may be changed. A list of these participants and the assumptions made under DRMI will be documented prior to unblinding of the study.

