## **1.2 Number of participants**

Approximately 240 participants will be enrolled/screened in order to achieve 160 eligible study participants randomly assigned to study intervention.

Up to Week 24, ie, prior to start of the extension period evaluating Q4W and Q8W dosing regimens, participants in both benralizumab 60 mg initial dose treatment arms will be considered as a single treatment group (total n=60), as will participants in both benralizumab 30 mg initial dose treatment arms (total n=60). Together with the 40 participants in the placebo treatment arm the above randomisation will provide a 3:3:2 ratio across the treatment group to assess the primary endpoint at Week 12.

This provides 90% power for statistical significance at the 2-sided 2.5% level within each induction dose comparison versus placebo if the assumed effect is a 4.7 point mean difference in change in ISS7 between benralizumab and placebo, assuming a SD of 6 for the change in ISS7 and a 10% dropout rate. These assumptions are in line with those for previous CSU trials ([Saini et al 2015](#)). The proposed sample size also provides a robust dataset to assess the key secondary endpoints, assess potential responders in sub-populations, and make a comparative assessment of the Q4W and Q8W dosing regimens in the maintenance period.

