### **8.1.5 Overall summary of analyses to account for missing data**

Forest plots will be used to show the primary analysis results along with the missing data sensitivity and alternative estimand analysis results.

It is noted that if the primary analysis is statistically significant, it is not necessarily expected that all sensitivity analyses will also give statistically significant results. If the results of the sensitivity analyses provide reasonably similar estimates of the treatment effect to the primary analysis, this will be interpreted as providing assurance that neither the lost information nor

the mechanisms which cause the data to be missing have an important effect on primary analysis conclusions. Based on these outputs and the drug's mechanism of action, the plausibility of the assumptions we make about missing data in the different analyses will be considered and described in the clinical study report.

The methodology described above to explore any potential impact of missing data for the ISS7 change at Week 12 endpoint may be repeated for other endpoints if required due to amount or pattern of missing data.

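### The Table 11 note fills placebo dropouts with the observed placebo mean, which contradicts the MAR multiple imputation that SAP Appendix 8.1 prescribes for the same sensitivity analysis

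*SAP*

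**What the plan says.** SAP 8.1.4 states that in the sensitivity analyses "missing data will be imputed using controlled sequential MI methods based on pattern mixture models". Item (a) defines MAR, arm by arm, as following the course seen in the participant's own arm. Item (b), DRMI, takes it that the course of benralizumab participants who "dropped out for a treatment related reason or severe non-compliance of protocol is similar to that of the placebo participants". For everyone else who leaves, the same item sets a different rule: "whereas the remaining participants who has dropped out are imputed assuming MAR".

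SAP 8.1.2 sets out the machinery for the whole full analysis set, with no exception for placebo. Step 1 produces 100 datasets by MCMC. In step 2 the remaining missing values "will be imputed using the regression method for the monotone pattern with adjustment for covariates as for the primary model". Step 4 uses Rubin's rule to "combine analysis results (point estimates and standard errors) from 100 imputations".

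The note under SAP Table 11 then says: "Participants in the placebo arm are imputed using the mean of the non-missing values in placebo arm".

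SAP 8.1.5 gives the reading rule. "If the results of the sensitivity analyses provide reasonably similar estimates of the treatment effect to the primary analysis", this is taken as assurance that the missing data have no important effect on the primary conclusions.

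**The concern.** These are two different procedures for the same participants. A MAR regression draw uses baseline, region and earlier visits, adds residual variation, and differs across the 100 datasets. A fill with the observed placebo mean uses none of that history and puts the same value in every dataset. No section reconciles the two, and a programmer who follows the note would code the fill.

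What is at stake is the robustness statement in 8.1.5. DRMI exists to show how far the estimate moves when flagged benralizumab dropouts are given a placebo-like course. If the placebo arm is handled differently at the same time, the distance between the DRMI and primary estimates also reflects the fill, which has nothing to do with the DRMI assumption. That can hide the departure or exaggerate it.

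**Working it through.** **Inputs from SAP 1.2:** 60 participants per dose against 40 on placebo, a difference of 4.7 points, 2-sided 2.5% level, and "assuming a SD of 6 for the change in ISS7 and a 10% dropout rate".

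**Assumed, not in the documents:** 10% dropout in each arm (so 4 of 40 on placebo), all after Week 4; equal SD at Weeks 4 and 12; correlation ρ = 0.6 between visits (range 0.4 to 0.8); the share of benralizumab dropouts flagged (all or half).

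**1. The plan's own figure.** After 10% dropout, 54 against 36: SE = 6 × √(1/54 + 1/36) = 1.291; 4.7/1.291 = 3.64; less the critical value 2.24 leaves 1.40, so power is 91.9% (91.1% by noncentral t). The stated 90% reproduces.

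**2. Shift caused by the fill.** Under MAR, a placebo dropout's expected Week 12 value is the completers' mean plus ρ times that participant's Week 4 distance from the completers. The fill drops the second term. With dropout fraction m and Week 4 gap d between placebo dropouts and completers, the contrast moves by m × ρ × d.
- d = 3: 0.10 × 0.6 × 3 = 0.18 points (0.12 at ρ = 0.4, 0.24 at ρ = 0.8).
- Purely random dropout: the average shift is 0. In a single trial, though, d has a chance SD of 6 × √(1/4 + 1/36) = 3.16, so the shift has SD 0.10 × 0.6 × 3.16 = 0.19.

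**3. Shift that DRMI is meant to produce.**
- All flagged, full effect already present at Week 4: 0.10 × 4.7 × (1 − 0.6) = 0.19 (0.28 and 0.09 at ρ = 0.4 and 0.8).
- All flagged, effect growing linearly to Week 12: 0.10 × (4.7 − 0.6 × 4.7/3) = 0.38 (0.41 and 0.35).
- Half flagged: 0.09 and 0.19.

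So a gap of 3 points yields a fill shift of about half to all of the intended shift if all are flagged, and about one to two times it if half are.

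**4. Simulation.** 1,500 runs per scenario, 20 imputations, sequential regression draws with parameter uncertainty, Rubin's rules, ρ = 0.6. Under score-dependent dropout d was about 3.5. Estimated benefit in ISS7 points:

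| Who leaves | Flagged | Effect by Week 4 | MAR | DRMI, proper draws | DRMI with fill |
|---|---|---|---|---|---|
| Worse scorers | all | full | 4.63 | 4.45 | 4.24 |
| Worse scorers | all | linear | 4.70 | 4.32 | 4.11 |
| Worse scorers | half | full | 4.72 | 4.63 | 4.42 |
| Worse scorers | half | linear | 4.68 | 4.49 | 4.29 |
| Better scorers | all | full | 4.66 | 4.47 | 4.69 |
| Better scorers | all | linear | 4.70 | 4.33 | 4.54 |
| Better scorers | half | full | 4.70 | 4.60 | 4.81 |
| Better scorers | half | linear | 4.71 | 4.53 | 4.74 |

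The fill shift is 0.20 to 0.22 throughout. In the first row it roughly doubles the departure from MAR (0.18 becomes 0.39); in the fifth it removes it (4.69 against 4.66). Under random dropout the simulated shift averaged 0.00 to 0.02 with SD 0.19 to 0.20. A separate simulation with the same inputs gave about 0.25 in either direction, with SD 0.21 under random dropout. With stronger dependence of dropout on the earlier score (one SD worse raises the log-odds by 1; ρ 0.5 to 0.7), the placebo mean is 0.28 to 0.38 points too favourable.

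**5. Standard error.** With the prescribed placebo donor for flagged benralizumab dropouts, the reported SE is 1.22 to 1.25 with the fill and 1.27 to 1.30 with proper placebo draws, 4 to 5% lower. The ratio of reported to empirical SE with the fill is 1.02 to 1.04 (all flagged) and 0.96 to 1.02 (half flagged), so it is not materially too small. A simpler formula that uses no earlier visits and imputes benralizumab from its own arm gives 1.214 against 1.291, about 6% lower.

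**The case against.** The note may be loose wording. Table 11 lists which arm supplies the imputation parameters, and only for benralizumab withdrawals, so the note could simply be adding that placebo is imputed from placebo. It names no visit and does not say whether the mean is adjusted, so it is hardly a complete algorithm. About 4 participants are involved. A shift of 0.18 to 0.22 is 4 to 5% of the 4.7 effect and under 0.2 of a standard error, and every fill estimate in the table is more than 3 standard errors from zero. The correlation, the Week 4 gap and the flagged share are assumed. SAP 4.2.6.3 makes these analyses conditional on the amount of missing data, which SAP 4.1 expects to be low.

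Most of this stands as a limit on size. It does not remove the conflict. The note names a statistic, the mean of the non-missing values, and not just a source arm; if only the source arm was meant, 8.1.4(a) already says so and the note is not needed. The relevant yardstick is the departure DRMI is built to measure, and against that the fill is not small. On conditionality, 8.1.4 itself says the additional analyses will be performed. If they run only when missing data are considerable, that is when the placebo rule counts most.

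**Conclusion.** The note is wrong as written: it contradicts 8.1.4(b) and 8.1.2 for placebo dropouts. Under the assumptions above, it moves the DRMI contrast by about 0.2 ISS7 points in either direction, against an intended shift of 0.09 to 0.38. It can therefore mask or exaggerate the result that 8.1.5 interprets. The largest total departure from MAR in the simulations was 0.59 points (4.70 to 4.11), of which 0.38 is the intended DRMI shift, against a standard error of about 1.25.

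The harm is confined to the robustness statement. The primary MMRM, alpha and power are untouched, and no reversed conclusion is claimed. The textual conflict is certain; its size depends on the assumed correlation, dropout timing and Week 4 gap. It should be corrected before unblinding.

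**What to change.** Delete the Table 11 note. In its place, state that placebo dropouts, like all non-flagged dropouts, are drawn by multiple imputation under own-arm MAR, conditioning on baseline, region and earlier visits, within the 100 imputations of 8.1.2.

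Two optional clarifications could go in at the same time. Step 2 of 8.1.2 could refer to the placebo-fitted regression that 8.1.4(b) and Table 11 already imply for flagged benralizumab dropouts. Step 3 could say that the merge with the WOCF dataset belongs to the substantial-rescue analysis of 4.2.6.3, the only analysis there that calls for WOCF. The main correction does not depend on either.

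The cost is SAP wording and a few lines of imputation code, with no new data. The DRMI interval becomes about 4 to 5% wider, and its estimate may move in either direction.
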